Title: fNIRS, Listening Effort, and Motivation

NCT number: NCT05893992

Document date: May 5th 2025

Design

The experiment was a one-factor (two-level) repeated measures within-subjects design. The independent variable was hearing aid program, comprising (1) standard and (2) DNN-based programs as factor levels. The dependent variables, like our previous design ¹⁷, were listening accuracy, subjective listening effort, and HbDiff. Listening accuracy was measured as percent of correctly repeated words. Listening effort was measured on a 7-point Likert scale ²⁷ (1-no effort, 2-very little effort, 3-little effort, 4-moderate effort, 5-considerable effort, 6-much effort, 7-extreme effort). HbDiff was measured using a prefrontal fNIRS system consisting of 6 active- and 2 short-channel optodes positioned across the prefrontal cortex.

Test materials

Stimuli consisted of sequences of up to five R-SPIN sentences presented in noise. Sequences, rather than individual sentences, were used to leverage the superpositioning of the response functions for each sentence in the sequence to enhance the overall temporal summation, thus increasing the SNR of the overall hemodynamic response ²⁸⁻³¹. Sequences varied in number of sentences so that participants would be unable to anticipate which word to repeat, forcing them to attend to the entire sequence. Sequences of three or more sentences were comprised of low-context sentences and were 18 or more seconds in duration. The shorter “decoy” sequences were comprised of one or two high-context sentences and were only included to create the impression that some sequences would contain only that number of sentences. The shorter high-context sequences’ data were not used for analysis. Noise consisted of multitalker babble and was gated on and off with each sentence. Speech was presented at individualized SNRs relative to the noise level, which was maintained at 70 dBA.

Equipment

Stimulus playback

The experiment was conducted in a double-walled, sound-attenuated booth. The participant was seated in the center of the booth. The listening paradigm was administered using a custom MATLAB script (version R2021b) running on a Windows computer located outside the booth, which controlled stimulus playback, recorded participant responses, and transmitted stimulus onset and offset markers to the fNIRS recording software. The Windows computer was connected to an RME Fireface UCX sound card, which routed the stimuli to two self-powered Genelec 8030C speakers positioned at 0 and 180 degrees relative to the participant's chair, each placed 1.3 meters away from the participant's head. Speech was presented from the front speaker while noise was presented from the rear speaker.

fNIRS device

Cerebral oxygenation was measured using an Octamon continuous-wave fNIRS device (Artinis Medical Systems, Netherlands) with six active optodes and two short channel optodes, consisting of eight LED diode emitters (wavelengths: 760 and 850 nm) and two photodiode detectors, sampled at 10 Hz. The light emitters and detectors were spaced approximately 3.5 cm apart, allowing penetration of about 1.75 cm into the cortex. The device was positioned over the participant's prefrontal cortex. The base of the fNIRS headband was aligned just above the nasion, ensuring the lower medial light emitters were symmetrically positioned around the FpZ coordinate ³². Recordings were transmitted via Bluetooth to the OxySoft software (version 3.2.70) on a Windows computer. The data were initially saved in .oxy4 format and later converted to .snirf format for analysis using MATLAB-integrated Homer3 scripts.

Hearing aids

The hearing aids used were Phonak Audéo I90-Sphere receiver-in-the-canal devices and coupled to participants' ears using occluding silicone power domes. The hearing aids were programmed using Phonak's proprietary gain formula and fine-tuned individually to NAL-NL2 targets by a licensed audiologist. Phonak's "Calm situation" and "Spheric speech in loud noise" programs, with all program features at default values, were used for the standard- and DNN-listening conditions, respectively. The standard-listening program is the hearing aid's default start-up program and implements omnidirectional microphones, speech enhancement and fast-acting compression; features common across manufacturers' standard-listening programs. The DNN-listening condition implements a combination of directional microphones DNN-based noise management, and slow-acting compression. Hearing aids were worn for the full duration of testing.

Procedure

SNR-50 search

Participants first determined the SNR at which they could correctly repeat 50% of the presented words (SNR-50). Individual SNR-50 measurements calibrated the "difficulty" of the task such that participants would perform equally despite differences in thresholds or other characteristics. Participants wore the hearing aids in the standard-listening program during the SNR-50 search procedure. This procedure followed modified hearing-in-noise-test (HINT) SNR adaptation rules and the manual adaptive level controls from the Oldenburg Matrix Test. In each SNR-50 run, participants listened to 20 low-context R-SPIN sentences and repeated the final word of each. The SNR was adjusted dynamically - decreasing following a correct response and increasing after an incorrect one. The noise level was maintained at 70 dBA and the speech level

varied systematically. The starting SNR was 8 dB. For the first five sentences, the SNR was adjusted in ± 4 dB steps, while the remaining sentences were adjusted in ± 2 dB increments. The SNR-50 was calculated as the mean SNR from sentences 12 to 20, plus the estimated SNR after the final trial. Each run consisted of 20 sentences randomly selected from the 25 available per R-SPIN list, with sentences from only one list used per run. Participants completed a total of three runs, with the average SNR-50+2 dB of the last two runs used for testing. The additional 2 dB were added to increase performance above chance so that participants would answer correctly more frequently and feel more motivated during testing. Throughout the task, the experimenter recorded participants' responses in real time to assess accuracy and trigger the next sentence. Across participants, the average SNR-50 was -0.6 dB (SD = 3.9).

fNIRS recording

The experimenter then placed the fNIRS device on the participant and paired it with the Oxysoft recording software. The signal quality was verified using the software's signal quality index algorithm, ensuring that the fNIRS recording SNR was above the noise floor and not saturated by ambient lighting. If the signal quality was insufficient, the experimenter adjusted the device fit.

Next, the experimenter provided the instructions for the main study task to the participants. The experimenter advised participants that they would hear sequences of sentences. Participants were instructed to repeat the last word of the last sentence in the sequence and then provide the number corresponding to their average listening effort rating for all the sentences in the sequence. Participants were then told that there would be a 30-second rest period between sequences and were asked to minimize movement and mind-wandering during baseline periods and testing. The

experimenter was able to postpone the start of the following sequence (therefore elongating the baseline recording) in case the participant moved during the rest period.

The study task consisted of testing blocks, with each block containing a total of eight events or sentence sequences: six sequences of three or more low-context sentences and two “decoy” sequences of one or two high-context sentences. Each sequence was separated by a 30-second silent baseline recording period. Each block comprised sentences taken from a single R-SPIN list not used in the SNR-50 task. Altogether, participants completed five blocks: a practice block and four test blocks. The practice block was completed using the standard-listening program and two of the remaining four test blocks were assigned to either the standard- or DNN-listening conditions, for a total 16 sequences per condition. Test block order and R-SPIN list/block assignment was randomized between participants.

Analysis

fNIRS data processing

The fNIRS processing pipeline resembled our previous study’s pipeline, which was adapted from Zhou et al., and was entirely implemented using MATLAB. The exception between our studies was that the current design incorporated short-channel subtraction. The fNIRS processing occurred as follows:

1. **Removal of step-like noise.** Brief losses of contact between the fNIRS headband and skin might produce abrupt steps in the fNIRS morphology and can negatively impact signal quality. These steps were removed by calculating the derivative of each channel’s intensity time series, and absolute values greater than two SDs over the derivative’s mean were zeroed. Channels were recalculated using the cumulative sum of the updated derivatives.

2. **Exclude channels of poor quality.** Signal quality was assessed using the scalp coupling index (SCI). The SCI extracts the heartbeat from the two fNIRS wavelengths by bandpass filtering between 0.5 and 1.5 Hz and then correlating the two filtered wavelengths. A poor correlation suggests that the fNIRS measurements did not accurately capture the heartbeat and would therefore not contain other meaningful physiological responses. Channels with an $SCI < 0.75$ were rejected, resulting in 11.5% of channels being rejected across participants.
3. **Conversion of light intensity to optical density.** Refer to Hupper et al.
4. **Correction of motion artifacts.** Movements during testing risk physical displacement of the optodes from the participant's head, risking noise in the data. The wavelet decomposition method was used to correct motion artifacts for any wavelet coefficients outside an interquartile range of 0.1.
5. **Conversion of optical density to hemoglobin concentration using the Modified Beer—Lambert law.** Refer to Delpy et al.
6. **Band-pass filter (0.01 – 1.5 Hz).** Low-frequency noise (such as drift) and high-frequency noise (such as breathing or heart rate) was band-pass filtered from the fNIRS signal.
7. **Short-channel correction:** Each channel underwent short-channel correction such that a general linear model was fit to the channel's fNIRS signal with the timeseries of the nearest short-channel (based on Euclidean distance) as the regressor. The physiological noise measured by the short-channel was regressed out of each channel's output.
8. **Band-pass filter (0.01 – 0.09 Hz).** An additional band-pass filter was applied to the data to remove any physiological noise missed prior to short-channel subtraction.

9. Averaging. HbO and HbR were calculated for each sequence of sentences. The hemodynamic response was measured as the average of 10 seconds following each sequence onset to the end of each sequence minus a 5-second baseline average prior to the start of the sequence. Ten seconds was chosen between sequence onset and measurement onset to allow for the hemodynamic response to reach its peak. Hemodynamic responses were then averaged across all low-context sequences for a given condition.

10. Data for analysis. The fNIRS response used for statistical analysis was calculated as the cerebral oxygen exchange ($HbDiff = HbO - HbR$). Three subregions, each containing averages across two optodes, were used for analysis. Lateral regions contained two peripheral optodes for each respective side and the lower medial region contained the two medial optodes.

Statistical modelling

Aligned with previous literature, subjective listening effort ratings and listening accuracy scores were averaged across trials resulting in a mean listening effort value and a mean accuracy score per participant. Afterwards, mean listening accuracy scores were transformed to rationalized arcsin units to reduce clustering of scores near ceiling performance. To assess the effect of the hearing aid program on subjective listening effort and on listening accuracy, two paired samples t-tests were conducted. A standardized effect size was calculated for each test using Cohen's d .

Blood oxygenation data ($HbDiff$) were modelled using multi-level modeling (MLM) because of the clustered data structure (i.e., high levels of covariance) due to the repeated measurement design. MLM estimates random effects for each cluster to provide unbiased model estimates (standard errors, regression coefficients, p-values). Furthermore, MLM is robust against cases of missing data, such as rejected channels falling below the SCI threshold⁴⁶. In contrast, an

Analysis of Variance (ANOVA) is a complete-case analysis where an entire participant's data would be removed if the participant had any missing data from rejected channels.

We conducted three MLMs with HbDiff as the outcome variable: an unconditional model and two a priori theory-driven models to assess the effect of the hearing aid program and whether the effect of the hearing aid program is moderated by subregions of the prefrontal cortex. The main predictor variable was the hearing aid program (standard vs. DNN) and an interaction term between the hearing aid program and prefrontal subregion (left lateral vs. lower medial vs. right lateral). Categorical variables (hearing aid program and prefrontal subregion) were dummy coded. Standard listening and the left lateral subregion were used as the reference group for the hearing aid program and prefrontal subregion, respectively. Simple slopes analysis was used to probe the interaction.

To assess which model best fit the data, a nested modeling approach was used. This approach adds predictor variables to the previous model and assesses if the additional predictors significantly improve the amount of variance explained by the model using a likelihood ratio test (LRT). The Akaike information criterion (AIC) was also used to assess model fit with lower AIC values indicating a better fit to the data.

All analyses were conducted in R version 4.4.2. MLMs were estimated using full information maximum likelihood (FIML) and conducted with the following packages: *lme4*, *lmerTest*⁴, *performance* and *interactions*. Paired samples t-tests were conducted using *stats* and Cohen's *d* was calculated using *lsr*. All statistical analyses were two-tailed tests with alpha of .05.

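### The model step meant to test moderation by subregion also brings in subregion itself (4 df together), so its LRT and AIC are not specific to moderation

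*Combined protocol and SAP*

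**What the plan says.** All of this is in the Statistical modelling section unless noted.

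- The model sequence: "We conducted three MLMs with HbDiff as the outcome variable: an unconditional model and two a priori theory-driven models". One predictor model is for the effect of hearing aid program, the other for whether subregion moderates that effect.
- The predictors: "The main predictor variable was the hearing aid program (standard vs. DNN) and an interaction term between the hearing aid program and prefrontal subregion". Subregion has three levels: left lateral, lower medial and right lateral.
- The coding: "Categorical variables (hearing aid program and prefrontal subregion) were dummy coded". Standard listening and left lateral are the reference levels.
- The comparison rule: "This approach adds predictor variables to the previous model and assesses if the additional predictors significantly improve the amount of variance explained", by LRT. In addition, "The Akaike information criterion (AIC) was also used to assess model fit", with lower values preferred.
- The follow-up: "Simple slopes analysis was used to probe the interaction".
- The data (fNIRS data processing, step 10): "Three subregions, each containing averages across two optodes, were used for analysis".

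The section prints no model formula and no LRT degrees of freedom. It lists no model with program and subregion but without their interaction, and it names no joint test of the product terms.

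**The concern.** An LRT between nested models tests everything added at that step. If subregion and its interaction with program enter together, a significant result says only that at least one of them matters. HbDiff may differ between lateral and medial prefrontal sites for reasons unrelated to the hearing aid program. Such a difference, equal under both programs, is not moderation, yet it counts in favour of the interaction model on both LRT and AIC.

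Moderation is one of the two HbDiff questions the plan sets, and LRT and AIC are its stated criteria for the best-fitting model. If either carries the conclusion, a plain regional difference could be reported as the program acting differently across the prefrontal cortex. There is also a cost in the other direction: a real interaction without average regional differences is harder to detect when its signal is spread over 4 df instead of 2.

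**Working it through.** The plan gives no figure to reproduce here. The degrees of freedom follow from the design; the error rates need assumptions, which are stated.

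**Degrees of freedom.** Inputs: program has 2 levels (Design) and subregion has 3 (Statistical modelling; step 10 of fNIRS data processing). Ranks of the fixed-effect design matrix over the 2 × 3 = 6 cells:

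| Model | Rank |
|---|---|
| Unconditional | 1 |
| Program | 2 |
| Program + subregion (not in the plan) | 4 |
| Program × subregion | 6 |
| Program + program:subregion, written with factors | 6 |

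The first step has 2 − 1 = 1 df. The second has 6 − 2 = 4 df: 4 − 2 = 2 for subregion and 6 − 4 = 2 for the interaction. Leaving the separate subregion term out of a factor formula changes nothing, since that formula still spans all six cell means.

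**Other readings.**
- Subregion already in the second model: the moderation step is a clean 2-df test, but the first step becomes 4 − 1 = 3 df and mixes program with region. With no program effect and a 0.5 SD regional shift, it rejects in 44%, 56% and 76% of runs (N = 15, 20, 30).
- Two hand-built product terms without subregion main effects: the step has 2 df but is still not specific. With no moderation and a 0.5 SD shift it rejects in 28%, 33% and 50%.

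None of these three-model readings makes both steps specific.

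**False moderation signals.** Assumed, because the document does not give them: N = 15, 20 or 30; a participant random intercept; residual SD 1; no program effect and no interaction; one region shifted by δ under both programs; complete data. With balanced data, LRT = 5N·ln(SSW_reduced/SSW_full), where SSW is the within-participant residual sum of squares. Critical values are 9.49 (4 df) and 5.99 (2 df). AIC prefers the larger model when LRT > 2 × 4 = 8. The product-term SE is √(4s²/N), with s² the ML residual variance. There were 6,000 simulations per setting; triplets are for N = 15, 20, 30.

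| Rule | No shift | δ = 0.25 SD | δ = 0.5 SD |
|---|---|---|---|
| 4-df LRT alone | 5-6% | 14%, 16%, 22% | 41%, 51%, 72% |
| AIC prefers interaction model | 10-11% | 21-31% | 53-81% |
| 4-df LRT and a product term with p < .05 | 3% | 5-6% | 8-9% |

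The 2-df interaction LRT rejects in 5-7% throughout, and the 1-df program LRT in about 5%. At 0.5 SD, the 4-df test is significant while the 2-df test is not in 36%, 45% and 67% of data sets.

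A closed-form check agrees. Two of the six cells are shifted by δ, so they lie 2δ/3 above the mean and the other four lie δ/3 below it. The sum of squares per participant is 2(2δ/3)² + 4(δ/3)² = 4δ²/3, and the noncentrality is λ = (4/3)Nδ². At δ = 0.5, λ = 5.0, 6.67 and 10.0, and the noncentral chi-square on 4 df gives 40%, 52% and 72%.

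**Sensitivity.**
- Missing subregions. Step 2 of fNIRS data processing reports channel exclusion, "resulting in 11.5% of channels being rejected across participants". If each participant-subregion is lost with that probability (both optodes failing together, a pessimistic case), the 4-df test rejects in 13-19% (0.25 SD) and 35-63% (0.5 SD). The 2-df test rejects in 5-7%, and the two-part rule in 5-6% and 8%. These runs used 4,000 simulations per setting.
- Participant-by-subregion effect of SD 0.5 or 1.0, present and fitted. The 4-df rates are 11-16% or 9-10% (0.25 SD) and 28-51% or 16-27% (0.5 SD), with 5-7% for the 2-df test.
- The same effect present but not fitted. At 0.5 SD the 4-df rates are 36-61% or 28-45%, and the 2-df test becomes conservative (3-4% or about 1%).

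**Power for a real interaction.** With no average regional difference, noncentrality 9.63 gives 80.0% on 2 df and 69.8% on 4 df; 12.65 gives 90.0% and 82.6%.

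**The case against.** The strongest reply is that the plan uses LRT and AIC to choose the best-fitting model and nowhere says that a significant last step establishes moderation. The interaction is examined through dummy-coded terms with stated reference levels and through simple slopes, and lmerTest can supply coefficient tests. In the full model, with main effects included, none of these is biased by a regional difference. An analyst who reads the product terms will largely avoid the error. The 8-9% left under the two-part rule reflects having two unadjusted contrasts: at least one product term has p < .05 in about 10-11% of null data sets whatever the regional shift. In addition, the formulas are not printed, the percentages rest on assumed inputs, and accuracy and effort, which use paired t-tests, are unaffected.

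Much of this stands. The fault lies in the LRT/AIC step, not in every inference about moderation, and the simulated rates are illustrations. But the plan does not make the product terms decisive. It describes simple slopes only as a probe of the interaction, and the formal criteria it names for comparing models are the LRT and AIC. The missing formulas do not rescue it either, since each three-model reading considered above leaves one step non-specific.

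**Conclusion.** The concern holds and should be fixed. On the most natural reading, the 4-df count follows directly from the 2 × 3 structure and depends on no assumed N or variance; the reading itself is an inference, because no formula is given. The direction of the error is also secure: an equal regional shift under both programs pushes LRT and AIC towards the interaction model.

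How often this misleads depends on inputs the document does not give. With complete data and only a participant intercept, the LRT read alone rejects in 14-22% at a 0.25 SD shift and 41-72% at 0.5 SD. A fitted participant-by-subregion effect lowers this, to 9-10% and 16-27% at SD 1.0. Requiring a significant product term as well brings it to 8-9% or less in the complete-data runs. The program effect keeps its own 1-df LRT on this reading and is not compromised.

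**What to change.** - Add a program + subregion model between the program and interaction models, and state each model's formula and the LRT degrees of freedom. The fixed-effect ranks become 1, 2, 4 and 6.
- Base any claim of moderation on the 2-df LRT of the interaction model against program + subregion, or on an equivalent joint 2-df test of the product terms in the full model.
- Treat AIC and simple slopes as supportive.
- Test program with a 1-df LRT.

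The cost is one extra model fit on the existing data; no new data are needed. If the analysis was already run this way, stating it is enough.
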